9.4.5 SAFETY ANALYSES

The stimulation questionnaire will be administered for the third and fourth session after stimulation. This questionnaire solicits ratings of 10 possible adverse effects associated with non-invasive brain stimulation, on a scale of 0 (absent), 1 (low), 2 (medium), 3 (high), 4 (very high). The side effects include that are expected to occur in some participants are headache, neck pain, scalp pain, muscle stiffness, skin tingling, skin itching, ringing noise, trouble concentrating, improved mood, and dizziness. Paired t-tests with random effect "participant" will be calculated per adverse effect to determine if there are any differences in adverse effect severity between sessions (delta-beta TMS, theta-gamma TMS, and arrhythmic TMS to dlPFC versus mPFC). Subjective severity per adverse effect will be described with mean and standard deviation. In addition, we will analyze the severity of each adverse event as determined by the Medical Monitor and PI. The process for determining the severity of an adverse event is detailed in Section 2.3.4.

A linear model with random effect "participant" will be calculated per adverse effect to determine if there are any differences in adverse effect severity between sessions (dlPFC and mPFC as categorical independent variables) and adverse effect severity as the continuous dependent variable. Subjective severity per adverse effect will be described with mean and standard deviation. In addition, we will analyze the severity of each adverse event as determined by the Medical Monitor and PI.

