stimulator output until a motor evoked potential (MEP) is generated: defined as a near-instantaneous increase muscle activity greater than 200 microvolts. Next, the intensity of single pulse TMS will be lowered until a MEP is generated on five out of ten pulses. This is defined as the motor threshold for the participant (Rossi et al. 2009). If the motor threshold cannot be determined via MEP, the experimenter will use visible twitches instead of MEP. Participants will receive 15 pulses of patterned TMS at 80% of their motor threshold during every trial. Patterned TMS takes three different forms (Figure 2). Delta-beta TMS delivers bursts of three pulses at 20 Hz (50 millisecond inter-pulse interval) with an inter-burst interval of 3 Hz (167 milliseconds). Theta-gamma TMS delivers bursts of three pulses at 50 Hz (20 millisecond inter-pulse interval) with an inter-burst interval of 5 Hz (200 milliseconds). As a control for the frequency-specificity of patterned TMS, arrhythmic TMS is delivered with a randomized inter-pulse intervals that are generated for each trial. The duration of arrhythmic TMS is randomly selected from a uniform distribution between the duration of delta-beta and theta-gamma TMS. The minimum inter-pulse interval will be 20 milliseconds. Between every train will be at least 11 seconds. An inter-train-interval of 11 seconds or greater allows for any residual effects of stimulation to return to baseline. This intensity, inter-pulse-interval, and inter-train-interval is well within the safety guidelines set forth for repetitive TMS (Wassermann, 1998; Rossi et al., 2009) and has been used in similar paradigms as the one described here. For example, Hermiller et al. 2020 delivered two seconds of theta-gamma patterned TMS (30 pulses per trial) at 80% of motor threshold (Hermiller et al. 2020). In addition, many other studies have delivered trains of TMS at higher intensities, upwards of 120% of motor threshold, on every trial of a cognitive task (Thut et al. 2011; Hanslmayr et al. 2014; Albouy et al. 2017)(Riddle et al. 2019; Riddle et al. 2020c; Sauseng et al. 2009). During a TMS session, participants will complete six blocks of 30 trials each. The participant will receive stimulation in either delta-beta, theta-gamma, or arrhythmic in a blocked design (the same stimulation is delivered for every trial in a block). The sequence of blocks will be randomized and counterbalanced such that each participant received each condition of TMS for 60 trials total. The third and fourth session of the experiment will be both be TMS sessions, where TMS is delivered to either the dorsolateral prefrontal cortex (dlPFC) or to medial prefrontal cortex (mPFC). The order and TMS sites will be randomized and counterbalanced across participants. Thus, at completion of the full experiment, participants will have received 12 blocks of 30 trials each of stimulation (180 trials per TMS session). In addition, two abbreviated blocks of TMS to mPFC and dlPFC will be administered at the end of the first session to assess for tolerability of TMS.

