7. STUDY INTERVENTION DISCONTINUATION AND PARTICIPANT DISCONTINUATION/WITHDRAWAL

7.1 DISCONTINUATION OF STUDY INTERVENTION

Discontinuation of stimulation during session 3 or session 4 means that study participation is halted and no other sessions are completed. If a clinically significant finding is identified after enrollment, the investigator or qualified designee will determine if any change in participant management is needed. Any new clinically relevant finding will be reported as an adverse event (AE).

The study intervention (i.e., patterned transcranial magnetic stimulation) will be discontinued for the following reasons:

- Any clinical adverse event (AE), laboratory abnormality, intercurrent illness or other medical condition, or situation occurs such that continued participation in the study would not be in the best interest of the participant.
- The participant meets any exclusion criteria (either newly developed or not previously recognized).

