9.3 POPULATIONS FOR ANALYSES

Every effort will be made to ensure all enrolled and randomized participants complete all study sessions as described in this protocol. For this study, enrolled eligible healthy participants will be randomized to receive stimulation to frontal and parietal cortex in a randomized sequence. If a participant completes session 4, then they will be included in all analyses moving forward.

As previously stated in **Section 7 Study Intervention Discontinuation and Participant Discontinuation/Withdrawal**, enrolled participants who do not get randomized will be replaced. If required, then we will create additional blocks of 10 randomized sequences. Therefore, we will collect data until 24 participants complete the study and are eligible for analysis.

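### The side-effect questionnaire analysis covers sessions 3 and 4 only and no safety population is defined, so session 1 ratings have no planned analysis and the paired t-tests drop anyone stopped in session 3

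*Combined protocol and SAP*

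**What the plan says.** Section 9.4.5 opens with "The stimulation questionnaire will be administered for the third and fourth session after stimulation" and rates ten effects from 0 to 4. It then gives two methods for the same ratings. The first paragraph has "Paired t-tests with random effect" for participant. The second has a linear model with a random participant effect, which "will be calculated per adverse effect to determine if there are any differences in adverse effect severity between sessions", with dlPFC and mPFC as the two levels. The section does not say which method governs. It also states "In addition, we will analyze the severity of each adverse event as determined by the Medical Monitor and PI", with no method, session or population attached.

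Section 9.3 is the only place where an analysis population is set: "If a participant completes session 4, then they will be included in all analyses moving forward". It adds: "Therefore, we will collect data until 24 participants complete the study and are eligible for analysis". No population based on exposure to TMS is defined.

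TMS starts before session 3. Section 4.3 describes two short blocks, one per site, that "will be administered at the end of the first session to assess for tolerability of TMS". The schedule of activities marks the stimulation questionnaire at sessions 1, 3 and 4. Section 4.1 describes it after the tolerability blocks, and 8.2 places it at the end of every stimulation session.

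On stopping, 7.1 says: "Discontinuation of stimulation during session 3 or session 4 means that study participation is halted and no other sessions are completed". Section 7.2 promises that drop-out reasons will be reported, and 8.3.4 records events from consent to the last day of participation.

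**The concern.** The questionnaire is the only safety measure with a planned statistical test, and its analysis is selected on the quantity that it measures. Session 1 acts as a tolerability filter, so the session 3 and 4 ratings describe people who have already passed it. Session 1 ratings are collected from everyone who receives the blocks, including those later excluded for task performance, yet no table or test uses them.

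A second selection follows in session 3. Someone stopped during dlPFC stimulation has no mPFC rating, and the reverse, so a paired test loses that person. These are ratings that would inform a comparison of tolerability between sites.

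The plan itself expects wider use of this information. Section 7.2 says that tolerability may interest other researchers and clinicians, and 9.4.7 would, after a seizure, set side effects against those of other TMS studies. Both uses need a denominator of everyone exposed.

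**Working it through.** **1. The plan's own figure.** The documents state no power or precision for safety. The number that limits the safety comparison is the 24 completers, which 9.2 supports for the secondary outcome with effect size 0.60, 80% power and a dependent t-test. With two-sided alpha 0.05, the noncentrality is 0.60 × √24 = 2.94 on 23 degrees of freedom. Power is 0.804, and 24 is the smallest n that reaches 80%, so the figure reproduces. A one-sided test would need 19.

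**2. Where each type of participant is counted, as written.**

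| Participant | Ratings that can exist | Paired t-test | Random-participant model | Other routes |
|---|---|---|---|---|
| Leaves after session 1 | Session 1 | No | No | Recorded adverse event; drop-out reason |
| Stopped in session 3 | Sessions 1, 3 | Dropped | Can be kept, unless limited to completers | Same |
| Stopped in session 4 | Sessions 1, 3, perhaps 4 | Only if rated at session 4 and counted as completing it | Can be kept, with the same caveat | Same |
| Completer | Sessions 1, 3, 4 | Yes | Yes | Same |

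**3. Do the other routes close the gap?** The relevant statements differ:
- 2.3.1 stops stimulation for an effect rated and confirmed as worse than moderate. The 0 to 4 scale in 2.3.4 runs absent, low, medium, high, very high and has no moderate grade.
- 2.3.4 and 4.1 link the structured adverse-event interview to a rating of very high (4).
- 6.1.2 says that common side effects, if experienced, are documented with that interview.

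Suppose that moderate means medium (2), and that a person is stopped at a rating of 3. Under 6.1.2 an interview documents the effect. Under 2.3.4 and 4.1 nothing requires one. On the second reading, a person stopped in session 1 or 3 could be absent from both the questionnaire comparison and the adverse-event analysis, and appear only as a drop-out reason.

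**4. Upper bounds on people outside a completer-only set.** Inputs: enrolment ceiling 50 and 24 completers (9.2); up to 30% excluded after session 1 for task performance (5.4).
- All exposed in session 1: 50 − 24 = 26, and 26/50 = 52%.
- After the task exclusion: 50 × 0.70 = 35; 35 − 24 = 11, and 11/35 = 31%.

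**5. Precision with zero events.** The one-sided 95% upper limit is 1 − 0.05^(1/n): 11.7% for n = 24, 8.2% for n = 35 and 5.8% for n = 50.

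**6. Sensitivity of a mean rating (assumed values, not in the documents).** If 24 completers average 0.5 and w people who stopped each rated 4, the mean is (24 × 0.5 + 4w)/(24 + w). For w = 1, 2, 3 and 5 this gives 0.64, 0.77, 0.89 and 1.10.

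**The case against.** A reader might infer that people who stop because of side effects disappear from the safety results altogether. The documents do not support that. Section 9.4.5 also analyses adverse-event severity without limiting it to sessions 3 and 4 or to completers. Events are recorded from consent, the schedule allows the interview at session 1, a very high rating triggers it, and drop-out reasons are reported.

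Other limits also stand:
- Completer-only safety is an inference. Section 9.3 says that completers are included; it does not say that others are excluded.
- The halt rule in 7.1 names sessions 3 and 4. It does not cover someone who stops in session 1, whose ratings go unused because no analysis takes them.
- The random-participant model, which can keep a person with one rating, is already planned.
- Leaving session 1 out of the site comparison is right. Both sites are stimulated and 4.1 describes one questionnaire afterwards, so its ratings cannot be assigned to a site.
- Safety is not a listed objective or outcome of this healthy-volunteer pilot.

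These points narrow the concern without removing it. The adverse-event analysis has no stated method or denominator, and its entry trigger varies between sections. Drop-out reasons are not planned as counts by session or site. Nothing says whether the model or the paired t-test governs, and no rule places non-completers in any analysis.

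**Conclusion.** The point holds for the questionnaire. Session 1 ratings have no planned analysis, no exposure-based safety set exists, and the paired t-tests exclude anyone stopped in session 3. The remaining routes cover these people only in part.

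The bounds of 26 of 50 and 11 of 35 are ceilings. They assume that enrolment reaches 50 and that all 50 receive the session 1 blocks; the second also takes the full 30% task exclusion. Both count every exit, including task performance, MRI failure and loss to follow-up. The documents give no rate of stopping for side effects, so it cannot be said by how much, or whether in fact, the reported ratings will be too low. The benefit of keeping people stopped in session 3 also depends on their having completed the form that day.

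The primary and secondary outcomes are unaffected. The change is worth making because it is cheap and the ratings are already in the schedule.

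**What to change.** Amend 9.3 and 9.4.5 as follows:
- Define a safety set of everyone who received any TMS, including the session 1 blocks, and state that 9.4.5 uses it.
- Tabulate session 1 ratings descriptively, without assigning them to a site.
- Tabulate session 3 and session 4 ratings by site, showing the number exposed as the denominator and the number with a rating.
- Count stops for side effects by session and, for sessions 3 and 4, by site.
- Make the random-participant linear model, fitted to all available session 3 and 4 ratings, the governing site comparison, and delete the paired t-tests.
- Reconcile 2.3.1, 2.3.4, 4.1 and 6.1.2 on what stops stimulation and what triggers the adverse-event interview, so that it is clear who enters the adverse-event analysis.

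The cost is SAP wording and slightly larger tables. No new measurement is needed.

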Risk of Injury and Discomfort: Transcranial magnetic stimulation has been cleared for use in the USA by the FDA. TMS (the methodology used in this experiment) has nothing to do with electroconvulsive therapy that applies many orders of magnitude higher stimulation current. The level of electrical stimulation produced by TMS is within the range of activity that is endogenous to the brain. Furthermore, the intensity of stimulation is calibrated to the sensitivity of the individual participant such that the level of stimulation is matched to that of naturally occurring activity. In order to monitor side-effects, we will be administering an adverse effects stimulation questionnaire after each stimulation session to determine whether these effects were experienced. Research personnel present during these sessions will also check with the participant periodically during the stimulation to see whether they are comfortable. If any side-effect occurs that is rated by the participant and confirmed by the researcher to be stronger than "moderate," the stimulation will be immediately stopped.

Risk of Psychological Discomfort: There is a psychological element in that some participants may become claustrophobic upon entering the small space of the MRI bore. To reduce psychological distress, participants are informed that they can withdraw consent and stop participation at any time. Participants are monitored throughout the MRI scans and can terminate the scan at any time by squeezing a ball held in the hand, and will be quickly removed from the MRI bore. There is additionally a risk of psychological discomfort from receiving transcranial magnetic stimulation (TMS). Due to the discomfort from receiving TMS and the proximity of the TMS coil to the face and head of the participant, this can result in psychological discomfort. Similar to MRI, participants are informed that they can withdraw consent and stop participation at any time. Participants are monitored throughout the TMS sessions and can stop receiving stimulation at any time by physically moving away from the TMS coil. The field of stimulation is less than a couple centimeters. Furthermore, researchers monitor the participant throughout stimulation and will check in with the participant approximately every 5 minutes between each task block.

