Risk of Injury from MRI: MRI will be conducted within the Biomedical Research Imaging Center (BRIC) at UNC Chapel Hill. The BRIC has a full-time staff that is well trained in the safety involved with MRI. Participants complete a contraindications form for MRI upon enrollment in each study. Any questions or concerns from the researcher can be addressed by the staff at the BRIC. In addition, the participant completes an additional screening form in the presence of the staff at the BRIC to further ensure that all safety concerns are addressed. The specific risks that are presented to the participant are avoided by effective screening. These risks include physical injury from the presence of metal within the body or in the environment when entering the magnetic field of the MRI. The strong magnetic field will pull metal towards the center of the field. Thus, it is imperative that all metal is removed from the body and any participants with metal within the body do not enter the field. The MR technicians at the BRIC maintain strict boundaries and screening via metal detector before entering rooms near to the MRI, adjacent to the MRI room, and the MRI room. This three-staged system is standard practice for MRI. Participants are provided with a medical gown and private changing room within the BRIC. This ensures that there is no chance that participants will enter the room with metallic objects in their pockets (e.g., phones or wallet). In addition, technicians screen participants and walk through a check list. Another risk from the MRI is the chance of a skin burn from clothing that contains metallic microfibers/particles. Thus, participants wear a medical gown to avoid the complication from modern athletic clothing technology. These risks are well-understood by the scientific community and extensive safety procedures are put in place by regulatory oversight that are maintained by the BRIC.

Risk of Transient Psychological Changes from TMS: There is a rare risk that TMS will result in alterations in mood, trouble concentrating, or sleepiness. These side effects are not commonly reported, but given the diversity of cognitive functions that the prefrontal cortex supports, TMS could potentially produce a transient change in the above listed cognitive functions.

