2.3.4 REFERRALS FOR MEDICAL FOLLOW-UP

To ensure participant comfort, a researcher will periodically check in with the participant about any side-effects he/she may be experiencing during each stimulation session. Following the conclusion of any session with TMS, the participant will receive an Adverse Effects Questionnaire to report on any of the side-effects he/she may have experienced. This questionnaire reports side-effects on a Likert scale (0 = Absent, 1=Low, 2=Medium, 3=High, 4=Very high). If the participant reports side-effects of “very high” intensity, the researcher running that session will administer the Structured AE Interview. The majority of studies using TMS do not record or document Adverse Events unless a serious adverse event occurs or an AE of significance occurs, but that threshold is determined by the researchers of that study. For example, two systematic reviews of adverse events for TMS in depression in older participants (Overvliet et al., International Journal of Geriatric Psychiatry 2021) and TMS in Parkinson’s disease (VonLoh et al., Parkinsonism and Related Disorders 2013) summarized the frequency of AEs and SAEs across many studies (Overvliet et al. 2021; VonLoh et al. 2013). From a careful read of these studies, it is clear that the threshold for what constitutes an Adverse Event on the mild end of the spectrum is not agreed upon. Thus, by using a Likert scale (0 = absent, 1 = low, 2 = medium, 3 = high, 4 = very high) and considering all instances of “very high” as the threshold to be considered an Adverse Event is a conservative approach that will result in documentation and follow-up interviews at a level greater than 95% of studies. The purpose of the Adverse Events Structured Interview is to acquire more information about the experience of the participant with respect to the onset of symptoms, the time course of the symptoms, presence of symptoms at baseline, and the potential cessation of symptoms at completion of the TMS session. This information is written up in a comprehensive document, the Adverse Events Report Form, that is then communicated to the Principal Investigator, [name], and the Medical Monitor, [name]. The PI and Medical Monitor then determine the severity of the Adverse Event and make a plan for follow-up with the participant if necessary. In the rare event that the researcher finds the adverse event to be unexpected, serious, or more than mild, then the researcher will immediately call the Medical Monitor to conduct an immediate assessment with the participant.

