The order of regions (dlPFC then mPFC, or mPFC then dlPFC) targeted by TMS in the third and fourth session will be randomized and counter-balanced. First, the participants will be fitted with a low-profile EEG net and EMG electrodes to the hand and forearm. For the third and fourth session, the same stimulator intensity will be used as in the first session. The structural MRI and regions of interest (dlPFC and mPFC) are imported into Localite neuronavigation software. The participant wears a 3D stereotaxic tracking headband and is registered to their structural MRI. Then, the TMS coil is targeted to either mPFC or dlPFC and the position of the coil relative to the head is recorded throughout the session. The participant performs the S-EEfRT as the patterned trains of TMS are delivered on every trial. Each block of the study is randomized to receive either delta-beta patterned (triplets of TMS pulses at 20 Hz every 3Hz), theta-gamma patterned (triplets of pulses at 50 Hz every 5 Hz), or an arrhythmic pattern (same number of pulses and duration with a random inter-pulse interval). After stimulation, a questionnaire is provided with common side effects of TMS. Based on the results of the stimulation side effects questionnaire, a structured adverse events interview is conducted to acquire more information regarding any side effects that were selected to be “very high” by the participant. This session will take approximately 2 hours.

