8.2 SAFETY AND OTHER ASSESSMENTS

1. A stimulation side effects questionnaire will be administered at the end of each stimulation session. This tool will be used as a safety measure and to collect data on the experience of the participant. The side effects questionnaire was adapted from studies in our group that used a different form of stimulation (transcranial electric stimulation), and was updated to remove questions that are not relevant to transcranial magnetic stimulation.
2. An MRI screening form will be administered over the phone during the phone screening and within 24 hours prior to the MRI session. This screening form is the standard provided by the Brain Research Imaging Center (BRIC) at UNC. During the phone screening, if there is any ambiguity in the eligibility of the participant, then we consult with the technicians at the BRIC for approval to conduct an MRI. Then, in the 24 hours prior to their MRI session, MR technicians at the center review a new screening form and confirm their eligibility to receive an MRI. Because this is the same form used in the screening for the experiment, the only way that a participant would fail to be eligible at this stage is if there was some change in their eligibility between sessions. While this is highly unlikely, the participant would be discontinued from participating.
3. A TMS screening form will be administered over the phone and at the start of each of the TMS session. If there is any ambiguity in the contraindications for the TMS form, then the medical monitor, [name], who is an epileptologist is consulted and final approval is acquired. Similar to the MRI screening form, it is highly unlikely that eligibility will change between sessions. Out of an excess of caution, we administer the TMS screening form at each TMS session to confirm that there is no contraindication, otherwise participation is discontinued.

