8.3.4 TIME PERIOD AND FREQUENCY FOR EVENT ASSESSMENT AND FOLLOW-UP

The occurrence of an adverse event (AE) or serious adverse event (SAE) may come to the attention of study personnel during study visits, or the study participant may report AE or SAEs outside of a scheduled study visit.

All AEs including local and systemic reactions not meeting the criteria for SAEs will be captured on the appropriate case report form (CRF). Information to be collected includes event description, time of onset, clinician's assessment of severity, relationship to study product (assessed only by those with the training and authority to make a diagnosis), and time of resolution/stabilization of the event. All AEs occurring while on study must be documented appropriately regardless of relationship. All AEs will be followed to

adequate resolution. Any medical condition that is present at the time that the participant is screened will be considered as baseline and not reported as an AE. However, if the study participant's condition deteriorates at any time during the study, it will be recorded as an AE. Changes in the severity of an AE will be documented to allow an assessment of the duration of the event at each level of severity to be performed. AEs characterized as intermittent require documentation of onset and duration of each episode.

Research personnel will record all reportable events with start dates occurring any time after informed consent is obtained until the last day of study participation. At each study visit, research personnel will inquire about the occurrence of AE/SAEs since the last visit. Events will be followed for outcome information until resolution or stabilization. All AEs including local and systemic reactions not meeting the criteria for SAEs will be captured on the appropriate case report form (CRF). Information to be collected includes event description, time of onset, clinician's assessment of severity, relationship to study product (assessed only by those with the training and authority to make a diagnosis), and time of resolution/stabilization of the event. All AEs occurring while on study must be documented appropriately regardless of relationship. All AEs will be followed to adequate resolution.

Changes in the severity of an AE will be documented to allow an assessment of the duration of the event at each level of severity to be performed. AEs characterized as intermittent require documentation of onset and duration of each episode.

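### The side-effect questionnaire has no item for sleepiness or lowered mood, so the planned per-effect comparison cannot register either

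*Combined protocol and SAP*

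**What the plan says.** **Instrument.** Section 9.4.5 states: "This questionnaire solicits ratings of 10 possible adverse effects associated with non-invasive brain stimulation". Each is rated from 0 (absent) to 4 (very high). The effects are "headache, neck pain, scalp pain, muscle stiffness, skin tingling, skin itching, ringing noise, trouble concentrating, improved mood, and dizziness". Section 8.2 says the form was "adapted from studies in our group that used a different form of stimulation", namely transcranial electric stimulation, and that questions irrelevant to TMS were taken out. It does not mention adding any.

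**Named risks.** Section 2.3.1, in its paragraph on transient psychological changes, says: "There is a rare risk that TMS will result in alterations in mood, trouble concentrating, or sleepiness".

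**Use of the ratings.** Section 9.4.5 plans, for each effect, a comparison of severity between the dlPFC and mPFC sessions, with means and standard deviations. It also plans an analysis of the severity of each adverse event as judged by the Medical Monitor and the principal investigator. Section 4.1 has a structured interview follow for "any side effects that were selected to be “very high” by the participant". Section 2.3.4 treats every such rating as an adverse event.

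**Timing.** The Schedule of Activities (1.3) places the questionnaire at sessions 1, 3 and 4. Section 9.4.5 analyses sessions 3 and 4.

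**The concern.** The risk section and the safety instrument do not match. A change in mood can go either way, but the form offers a rating only for the favourable direction, and it lists that rating among the adverse effects. Sleepiness cannot be rated at all. Under the rule in 2.3.4, a very high rating of improved mood counts as an adverse event, while lowered mood has no rating that could reach that threshold.

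The practical risk lies in how the safety table will be read. The trial stimulates prefrontal targets in circuits that section 2.1 links to anhedonia, and section 4.2 expects the results to inform later work in depression. A per-effect table with one mood row, in the favourable direction, and no sleepiness row could be taken as evidence that neither harm occurred, when neither was rated. Any interim descriptive review of the safety measures under 9.4.7 would have the same gap in its ratings. Ratings not taken after stimulation cannot be recovered later.

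**Working it through.** This is a check of content, not of power.

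**Step 1. Reproduce the stated count.** Section 9.4.5 gives 10. Counting its list: headache (1), neck pain (2), scalp pain (3), muscle stiffness (4), skin tingling (5), skin itching (6), ringing noise (7), trouble concentrating (8), improved mood (9), dizziness (10). The count agrees, so the list reads as the complete set of rated effects and not as examples from a longer one.

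**Step 2. Set the risks in 2.3.1 against the items in 9.4.5.**

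| Psychological risk in 2.3.1 | Item in 9.4.5 | Coverage |
|---|---|---|
| Change in mood, no direction given | Improved mood | Favourable direction only |
| Trouble concentrating | Trouble concentrating | Full |
| Sleepiness | None | None |

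Of three named risks, one is fully rated, one is rated in one direction, and one is not rated. Trouble concentrating touches on alertness but does not measure sleepiness.

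**Step 3. Follow a missing item through the plan.** With no rating there is no mean or standard deviation, no dlPFC-versus-mPFC comparison for that effect, and no very high score to trigger the structured interview.

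**Step 4. Count the forms.** 24 completers × 2 analysed sessions = 48 forms. Session 1 adds one form per participant who has the tolerability test; 9.4.5 does not analyse it.

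**Step 5. Check whether another scheduled scale fills the gap.** Section 8.1.3 says the STAI and the SHAPS are taken at each session, whereas the Schedule of Activities shows both at session 1 only. Neither enters the analysis in 9.4.5, so neither supplies the missing comparison.

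**Step 6. Apply the change.** 10 + 2 = 12 items. All three risks would then be rated, with mood rated in both directions.

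**The case against.** The strongest reply is that the questionnaire is not the trial's only safety source.

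- Section 8.3.4 says: "At each study visit, research personnel will inquire about the occurrence of AE/SAEs since the last visit". All adverse events go on a case report form and are followed.
- Sections 2.3.1 and 2.3.4 add check-ins during stimulation, about every five minutes between blocks, open to any side effect.
- A very high rating is not the only way to an adverse event record. Section 2.3.4 has the researcher call the Medical Monitor about an event that is unexpected, serious or more than mild. Section 6.1.2 documents common side effects by structured interview without requiring that rating. Section 7.1 reports new clinically relevant findings as adverse events.
- Section 9.4.5 analyses adverse event severity.

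All of this stands. A reader might infer that the safety results as a whole cannot show lowered mood or sleepiness, that the questionnaire is the only solicited safety measure, or that a severe drop in mood could not reach an adverse event record. The documents do not support any of these. A reader might also say that the protocol names worsened mood as a risk. It does not: it names a change in mood, and worsening is one direction of that.

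These routes do not, however, produce a 0–4 score or a between-session comparison. The visit inquiry looks back to the previous visit, and session 4 is the last, so effects that begin after it depend on the participant reporting them.

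Three further replies carry weight. The sentence in 2.3.1 that the questionnaire will "we will be administering an adverse effects stimulation questionnaire after each stimulation session to determine whether these effects were experienced" sits in the paragraph on injury and discomfort, so the protocol does not promise that the form covers the psychological risks. The form itself is not in the documents, so a free-text field cannot be excluded. And the clinical relevance is limited: section 2.3.1 calls these effects rare and not commonly reported, section 7.2 says tolerability here likely does not carry over to clinical use, and the comparison is between two active sites. With 24 completers and no reports of an effect, the one-sided 95% upper bound on its frequency is still 1 − 0.05^(1/24) = 11.7%. Two added items would improve description; they would not establish safety.

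**Conclusion.** The concern holds for the questionnaire and its per-effect analysis. As written, the graded ratings and the dlPFC-versus-mPFC comparison cannot register sleepiness or lowered mood, although 2.3.1 lists sleepiness and change in mood as risks. Both could still be found through open inquiry, in-session check-ins and the adverse event severity review, without a graded comparison between sessions.

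This rests on two assumptions: that the 10 listed effects are the whole rated set, which the matching count supports, and that any free-text field on the form would not enter the per-effect analysis, which 9.4.5 gives no reason to expect.

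Severity is low. The instrument's content can be improved cheaply; no commitment has been broken, and the efficacy analyses are unaffected.

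**What to change.** Add worsened mood and sleepiness, on the same 0–4 scale, wherever the questionnaire is given (sessions 1, 3 and 4). Include both in the per-effect analysis in 9.4.5 for sessions 3 and 4, and change the stated number of items from 10 to 12. Keep improved mood, but report it beside worsened mood as an item on the direction of mood change.

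The cost is two short ratings per form, a revised form and a small edit to 9.4.5. Stimulation, visit schedule, sample size and efficacy analysis do not change. Participants who have already used the old form will lack the two items; report the number rated for each item so that the smaller denominator is visible.
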